4.1.3 Method of assigning patients to treatment groups

Only 1 dose group is planned in this trial, and it is unnecessary to randomize subject.

The allocation process of subjects will be performed on day 1 prior to study drug administration. Once a subject number has been assigned, it cannot be reassigned to any other subject.

4.1.4 Drug assignment and administration of doses for each patient

The drug product, idarucizumab (50 mg/mL) is administered solution for infusion without dilution. Trial medication will be filled into an infusion solution bag and will be used for iv infusion.

The treatments to be evaluated are as outlined in [Table 4.1.4: 1](#) below.

The trial medication will be prepared according to the preparation instructions by authorized personnel at the trial site. For the correct preparation of idarucizumab intravenous solutions, see the ISF.

Table 4.1.4: 1

Dose group

Dose group	1	
Dose [mg]	2500	+ 2500
Total volume of idarucizumab in infusion bag to be prepared [mL]		150
Infusion volume of idarucizumab to be applied [mL]	50	+ 50
Infusion time [min]	5	+ 5
Infusion volume rate [mL/h]	600	+ 600

For the dose group, following an overnight fast of at least 8 hours for the morning dose, and at least 2 hours for the evening dose, dabigatran etexilate will be administered with 240 mL of water in the sitting position under supervision of the investigator or designee. BI655075 will be administered under supervision of the investigator or designee approximately 2 hours after the last dabigatran administration on day 11.

- Subjects are not allowed to lie down during the 2 hours following dabigatran etexilate administration (i.e. no declination of the upper body of more than 45 degrees from upright posture) unless supine position is required for clinical assessments. They are not allowed to sleep.
- On day 4: from 1 hour before dabigatran etexilate intake until 4 hours post-dose, liquid intake is restricted to the fluid administered with the drug and additional 240 mL of water at approximately 1 hour 30 minutes and 4 hours post-dose, respectively (mandatory for all subjects). From 4 hours post-dose until 24 hours post-dose, water intake is restricted to 3000 mL.

- On day 11: from 1 hour before dabigatran etexilate intake until 4 hours post-dose, liquid intake is restricted to the fluid administered with the drug and additional 240 mL of water at approximately 1 hour 30 minutes (before BI655075 administration) and 4 hours post-dose, respectively (mandatory for all subjects). From 4 hours post-dose until 24 hours post-dose, water intake is restricted to 3000 mL.

Standardised meals will be served at 2, 5 and 9 hours following morning drug administration on days 1, 2, 3, 8, 9, 10 and at 4 hours and 9 hours post morning dose on days 4, 11.

Additionally, snacks will be served 2 hours after the evening intake of dabigatran on days 1-3, 8-10 and 13 hours post dose on day 11.

4.1.5 Blinding and procedures for unblinding

4.1.5.1 Blinding

This open-label, Phase I trial will be handled in an open fashion throughout (that is, during the conduct, including data cleaning and preparation of the analysis).

4.1.5.2 Unblinding and breaking the code

Not applicable.

4.1.6 Packaging, labelling, and re-supply

The investigational products will be provided by BI or a designated CRO. They will be packaged and labelled in accordance with the principles of Good Manufacturing Practice (GMP).

For details of packaging and the description of the label, refer to the ISF.

4.1.7 Storage conditions

Drug supplies will be kept in their original packaging and in a secure limited access storage area according to the recommended storage conditions on the medication label. A temperature log must be maintained for documentation.

If the storage conditions are found to be outside the specified range, the local clinical monitor (as provided in the list of contacts) must be contacted immediately.

The trial medication must be stored securely, e.g. in a locked cupboard or at a pharmacy. It may only be dispensed to trial subjects according to the protocol by authorised personnel at the trial site.

All unused medication must be returned to the sponsor. Receipt, usage and return must be documented on the respective forms. Account must be given for any discrepancies.

4.1.8 Drug accountability

The Investigator < and/or > Pharmacist < and/or > investigational drug storage manager will receive the investigational drugs delivered by the sponsor when the following requirements are fulfilled:

- Approval of the trial protocol by the IRB / ethics committee
- Availability of a signed and dated clinical trial contract between the sponsor and the head of the investigational site,
- Approval/notification of the regulatory authority, e.g. competent authority,
- Availability of the curriculum vitae of the principal Investigator,
- Availability of a signed and dated clinical trial protocol

The Investigator < and/or > Pharmacist < and/or > investigational drug storage manager must maintain records of the product's delivery to the trial site, the inventory at the site, the use by each subject, and the return to the sponsor or warehouse / drug distribution centre or alternative disposal of unused products. If applicable, the sponsor or warehouse / drug distribution centre will maintain records of the disposal.

These records will include dates, quantities, batch / serial numbers, expiry ('use- by') dates, and the unique code numbers assigned to the investigational product and trial subjects. The Investigator / Pharmacist / investigational drug storage manager will maintain records that document adequately that the subjects were provided the doses specified by the CTP and

reconcile all investigational products received from the sponsor. At the time of return to the sponsor< and/or >appointed CRO, the Investigator / Pharmacist / investigational drug storage manager must verify that all unused or partially used drug supplies have been returned by the clinical trial subject and that no remaining supplies are in the Investigator's possession.

4.2 OTHER TREATMENTS, EMERGENCY PROCEDURES, RESTRICTIONS

4.2.1 Other treatments and emergency procedures

There are no special emergency procedures to be followed.

Primarily, no concomitant therapy will be allowed. However, in case of AEs in need of treatment, symptomatic therapy according to the judgement of the investigator will be permitted. All concomitant and/or rescue therapies will be recorded on the appropriate pages of the electronic case report forms (eCRFs).

In the case of AEs the subjects will be treated as necessary and, if required, kept under constant supervision at the trial site or transferred to hospital until such time that all the results of the evaluations have returned to a medically acceptable level.

It is of major importance for group treated with dabigatran etexilate to monitor the subjects for bleeding events.

In case of unexpected minor bleeding local haemostasis has to be initiated as medically required and careful monitoring of the subject is needed. For minor bleedings a watchful waiting approach is generally appropriate.

If a subject experiences a major bleed, the trial medication should be stopped and the bleeding treated according to local practice. This will generally involve coagulation testing (aPTT, TT, fibrinogen, platelet count), transfusion support, and surgical haemostasis as indicated.

According to the experience with bleeding events in other circumstances, some general recommendations can be given:

The administration of aminocaproic acid (a potent inhibitor of fibrinolysis) and of vasopressin analogues (leading to increased circulating levels of pro-coagulant factor VIII and von Willebrand factor) can be useful in certain circumstances of bleeding events. In preclinical trials with direct thrombin inhibitors the administration of recombinant factor VIIa or Activated prothrombin complex concentrates (e.g., FEIBA) has been found to be useful and can also be considered. Consideration may be given to the use of fresh frozen plasma and it may also be possible to remove dabigatran by haemodialysis.

The use of these agents may be discussed in case of an overdose of dabigatran. Due to the unpredictable effect of these therapies a careful balance against potential untoward effects has to be done on an individual basis.

4.2.2 Restrictions

4.2.2.1 Restrictions regarding concomitant treatment

Use of concomitant medications which affects the clotting parameters or is known to have PK interaction with dabigatran (e.g. acetylsalicylic acid, clopidogrel, ticlopidine, dipyridamole or aspirin/dipyridamole, warfarin, other Vitamin K-dependent anticoagulants, or known P-gp inhibitors/inducers) is not permitted since the combination of any of these agents with dabigatran may increase the risk of bleeding. Non-steroidal anti-inflammatory drugs (NSAIDs) and systemic corticosteroids are restricted, but may be used if clinically indicated.

4.2.2.2 Restrictions on diet and life style

Subjects should abstain from alcoholic beverages for at least 48 hours prior to first trial drug administration and until EOT visit examination and from smoking during the whole domicile period.

Methylxanthine-containing drinks or foods (coffee, tea, cola, energy drinks, chocolate, etc.) are not permitted 24 hours preceding the administration of trial medication and until the end

of plasma and urine PK sampling. Citrus fruits, in particular grapefruits and Seville oranges (sour or bitter oranges), and their juices as well as products containing St. John's wort (*Hypericum perforatum*) are not permitted 5 days before the administration of trial medication and until the end of plasma and urine PK sampling of the respective visit. The subjects are instructed not to use any additional concomitant drug or undergo any medical treatment or any surgical procedure 14 days prior to, during and until EOT visit without having informed the investigator or his/her deputy.

While admitted to the trial site the subjects are restricted from consuming any foods or drinks other than those provided by the site staff.

On all days when laboratory sampling is planned, subjects will appear after an overnight fast, however, at least for 6 hours on day -1 (1 day prior to the first trial day). Subjects must not expose themselves to direct sun light or use artificial solaria during participation in the clinical trial.

Excessive physical activity should be avoided during the course of the trial (competitive sport etc.).

In order to minimize the risk of acquiring a potential bleeding, all subjects planned to be enrolled in the groups with dabigatran treatment, will be reminded of the following precautions:

- Be alert to early signs of bleeding such as occurring of bluses, pain in the abdomen, lower back or side. If any of these symptoms occur, subjects have to get in touch with the trial physician immediately
- Take care to avoid cuts or other injuries. Be especially careful when using knives, razors, nail clippers and other sharp objects. Check with the trial physician for the best ways to clean the teeth and mouth without injuring the gums.

4.2.2.3 Restrictions regarding women of childbearing potential

Women of childbearing potential must use the contraception methods described in the subject information.

4.3 TREATMENT COMPLIANCE

Subjects who are non-compliant, e.g., they do not appear for treatment or violate the restrictions, may be withdrawn from the trial and the eCRF will be completed accordingly (for further procedures see [Section 3.3.4.1](#)). If subject withdraws during Visit 2 (after administration of the trial drug), a complete post-examination will be performed.

Compliance will be assured by administration of all trial medication under supervision of the investigator or designee. The measured plasma concentrations and/or urinary excretion will provide additional information about compliance.

5. VARIABLES AND THEIR ASSESSMENT

A total amount of approximately 328 mL blood will plan to be taken per subject until EOT visit of the trial. In addition to that, 4 mL blood will plan to be taken per subject for ADA measurements at FU1 and FU2 after idarucizumab administration.

5.1 TRIAL ENDPOINTS

5.1.1 Primary Endpoints

The following pharmacokinetic parameters will be determined as Primary endpoints, if feasible: For idarucizumab: C_{max} , $AUC_{0-\infty}$, Ae_{0-72}

The following pharmacodynamic parameters will be determined as Primary endpoints:

For dTT: $AUEC_{above,2-12}$ on day 4 and day 11

5.1.2 Secondary Endpoints

The following pharmacokinetic parameters will be determined as secondary endpoints, if feasible:

For sum dabigatran: $Ae_{0-74,ss}$ on day 4 and day 11

For unbound sum dabigatran: $AUC_{2-12,ss}$ on day 4 and day 11

5.2 ASSESSMENT OF EFFICACY

Efficacy measurements will not be performed.

The PD parameters listed in [Section 5.1.1](#) and [5.1.3](#) will be used to explore the effect of idarucizumab on coagulation parameters.

5.3 ASSESSMENT OF SAFETY

5.3.1 Physical examination

Physical examination (for the time points see Flow Chart) will include an examination of general appearance, skin, lungs, heart, abdomen, lymph nodes, extremities and basic nervous system evaluation.

Information about the physical examination must be present in the source documentation at the trial site. Significant findings made after the start of trial drug which meet the definition of an AE must be recorded as the AE in eCRF.

5.3.2 Vital Signs

Systolic and diastolic blood pressure (BP) as well as pulse rate (PR) will be measured after at least 5 minutes of rest in the supine position. All recordings shall be made using the same BP recording instrument on the same arm (see [Flow Chart](#) for time points). Body temperature (BT) will be measured at the time points described in the Flow Chart. All measurements will be evaluated and signed by the investigator or designee. Any abnormalities considered significant by the investigator will be carefully monitored and reported as AEs and if necessary, the subject will be removed from the trial and medically treated. A description of the overall assessment, i.e. normal or abnormal (clinically significant or clinically not significant) will be made. All measurements will be documented and kept at the site as the source data.

5.3.3 Safety laboratory parameters

The laboratory tests listed in [Table 5.3.3: 1](#) will be performed at the trial site.

A total amount of approximately 80 mL blood will plan to be taken per subject during the whole course of the trial for laboratory parameters. This amount may be exceeded if unscheduled (additional) monitoring of laboratory results is warranted.

The respective reference ranges will be provided in the ISF (see [Flow Chart](#) for time points of laboratory blood sampling).

Urine sediment will only be done if there is a positive finding on the urinalysis. The tests listed in [Table 5.3.3: 1](#) constitute lab tests adopted in the exclusion criteria. These tests may be repeated as required. The results will not be included into the report, although the results are filed at the investigator's site as source documents (except for Albumin, IgG, alpha-Microglobulin).

To encourage compliance, a breath alcohol test and urine drug screen will be performed at screening, on admission and may be performed at any time during the trial by the discretion of an investigator or designee. The results will not form part of the report, although the results are filed at the investigator's site as source documents.

Urine protein and urine glucose will be performed qualitative and quantitative measurement. The results of the qualitative analysis will not be included into the report, although the results are filed at the investigator's site as source documents.

Laboratory data will be entered into the eCRF.

Fecal occult blood test will be performed at Screening (Visit 1). Subjects are allowed to collect the specimen in a tube at home and bring the tube at the trial site. The results will not form part of the report, although the results are filed at the investigator's site as source documents.

Pregnancy Testing

A urine pregnancy test will be performed locally on all women of child bearing potential at screening and EOT visits.

Table 5.3.3: 1 Routine laboratory tests

Category	Test name
Haematology	Haematocrit (Hct) Haemoglobin (Hb) Red Blood Cell Count/Erythrocytes Reticulocyte Count White Blood Cells/Leucocytes Platelet Count/Thrombocytes
Diff. Automatic (relative count)	Neutrophils Eosinophils Basophils Monocytes Lymphocytes
Coagulation	Partial Thromboplastin Time (=aPTT) Prothrombin Time (Quick and INR) Fibrinogen
Enzymes	AST/GOT, SGOT ALT/GPT, SGPT Alkaline Phosphatase (AP/ALP) Creatine Kinase (CK) CK-MB if CK is elevated Gamma-Glutamyl Transferase (GGT/γ-GT) Lactic Dehydrogenase (LDH) Lipase ¹ Amylase ¹
Hormones ¹	TSH fT3, fT4
Substrates	Glucose Creatinine Bilirubin Total Bilirubin Direct Protein, Total Protein electrophoresis ¹ Albumin Alpha-1-Globulin Alpha-2-Globulin Beta-Globulin Gamma-Globulin C-Reactive Protein (CRP) Uric Acid Cholesterol, total Triglycerides
Electrolytes	Calcium Sodium Potassium

Table 5.3.3: 1 Routine laboratory tests (cont.)

Category	Test name
Fecal occult blood test ^{1, 2}	Blood/Erythrocytes
Urinalysis (Stix)	Urine Nitrite Urine Protein (qualitative ² and quantitative test) Urine Glucose (qualitative ² and quantitative test) Urine Ketone Urobilinogen Urine Bilirubin Urine RBC/Erythrocyte Urine WBC/Leukocytes Urine pH Urine creatinine ¹
Low molecular weight proteins	Albumin, IgG, Alpha-Microglobulin
Urin-Sediment (microscopic examination) (only if urinalysis [stix] will be positive)	Urine Sediment Bacteria Urine Cast in Sediment Urine Squamous Epithelium Cells Urine Sediment RBC/Erythrocytes Urine Sediment WBC/Leucocytes
Drug Screening (Urine) ^{1, 2}	Phencyclidine Benzodiazepine Barbiturates Opiates Cocaine Amphetamines Tetrahydro-cannabinol Tricyclic antidepressant
Infectious Serology ^{1, 2}	Hepatitis B Surface Antigen (qualitative) Hepatitis B HBc Antibody (qualitative) Hepatitis C Antibodies (qualitative) HIV-1 Antibody (preliminary screening) Syphilis test (TP antibody method)

1. Only at screening.

2. Results will not be part of the report.

5.3.4 **Electrocardiogram**

For the assessment of possible drug induced electrocardiographic changes and/or safety monitoring 12 lead resting ECGs (I, II, III, aVR, aVL, aVF, V1 - V6) will be recorded using a ECG machine.

In order to assure high quality recordings at comparable resting phases of the subjects the subjects will be laid down in supine position for at least 5 minutes prior to each of the intended time points (see [Flow Chart](#)) in order to achieve a stable heart rate at rest. The site personnel will be instructed to assure a relaxed and quiet environment and that all subjects are at complete rest during the recordings.

Triple of ECGs 1 to 3 minutes apart will be recorded prior to idarucizumab administration on day 11 only.

In order not to confuse ECG recording, PK/PD samples should be taken after performing the ECG.

ECG recordings at planned time points may be repeated for quality reasons like alternating current artifacts, muscle movements and electrode dislocation. In this case the repeated ECG recordings may be used for the planned analysis.

All locally printed ECGs will be evaluated by the trial investigator or designee. Additional (unscheduled) ECGs can be recorded for safety reasons at any time based on the judgment of the investigator.

Clinically relevant abnormal findings will be reported as adverse events. Any ECG abnormalities will be carefully monitored and if necessary the subject will be removed from the trial and medically treated.

For the inclusion/exclusion of a subject and for the assessment of cardiac safety during the trial the QT and QTc values generated by the ECG machines or their manual corrections by the investigators will be used.

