3.3.2 Inclusion criteria

Healthy males and females according to the following criteria:

1. Age ≥ 18 and Age ≤ 45 years at screening
2. Healthy male and female based upon a complete medical history, including vital signs (BP, PR, and BT), 12-lead ECG and clinical laboratory tests. Women of childbearing potential¹ must be ready and able to use highly effective methods of birth control per ICH M3 (R2) that result in a low failure rate of less than 1% per year when used consistently and correctly. A list of contraception methods meeting these criteria is provided in the patient information.
3. Body weight ≥ 50 kg with BMI range ≥ 19.0 and < 24.0 kg/m² at Visit 1.
4. Signed and dated written informed consent in accordance with GCP and local legislation prior to admission to the trial.

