20. A marked baseline prolongation of QT/QTc interval (e.g., repeated demonstration of a QTcF interval >450 ms)
21. A history of additional risk factors for TdP (e.g., heart failure, hypokalemia, family history of Long QT Syndrome)
22. Positive HIV test result at screening examination

23. Positive testing for Hepatitis B Antigen and/or a positive Hepatitis C antibody test result at screening examination
24. Subjects considered unsuitable for inclusion by the investigator, e.g. are unable to understand and comply with trial requirements, or have any condition which in the opinion of the investigator would not allow safe participation in the trial.
25. Subjects who do not agree to minimize the risk of female partners becoming pregnant from the first dosing day until 12 weeks after the trial completion. Acceptable methods of contraception comprises barrier contraception and a medically accepted contraceptive method for the female (intra-uterine device with spermicide, hormonal contraceptive since at least 8 weeks)
26. History or evidence of blood dyscrasia, haemorrhagic diathesis, severe thrombocytopenia, cerebrovascular haemorrhage, bleeding tendencies associated with active ulceration or overt bleeding of gastrointestinal, respiratory or genitourinary tract or any disease or condition with haemorrhagic tendencies (e.g. cerebral aneurysm, dissecting aorta, CNS trauma, retinopathy, nephrolithiasis)
27. Abnormal values for PT, aPTT and thrombocytes considered by the investigator or one of the co-investigators to be clinically relevant
28. Creatinine and estimated glomerular filtration rate (GFR) outside the normal range
29. Evidence of proteinuria
30. Women who are pregnant, nursing, or who plan to become pregnant while in the trial

A record of all subjects screened, in- or excluded, will be maintained.

For trial restrictions, see [Section 4.2](#).

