6. INVESTIGATIONAL PLAN

6.1 VISIT SCHEDULE

Exact times of measurements outside the permitted time windows will be documented. Time windows are permitted as follows:

- General Physical examination: at screening (2 to 28 days prior to the first trial day) and at the EOT (16 to 24 days).

For planned individual plasma concentration sampling times and urine collection intervals see the [Flow Chart](#). While these nominal times should be adhered to as closely as possible, the actual sampling times will be recorded in eCRF and used for determination of PK parameter.

The designation “before” on trial days refers to the time period of within 2 hours before drug administration (planned time -2:00) (see Flow Chart), i.e. trial measurements and assessments scheduled to occur “before” have to be performed and completed within 2 hours prior to drug administration.

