6.2 DETAILS OF TRIAL PROCEDURES AT SELECTED VISITS

6.2.1 Screening and run-in periods

Screening Period

After the subjects have been informed on the trial, all subjects will have given their written informed consent in accordance with GCP and the local legislation prior to admission to the trial.

For the physical and laboratory examinations during the screening visit, see [Sections 5.3](#), the screening investigations will be performed on 2 to 28 days prior to the first trial drug administration.

Drug and virus screening will be performed (for details see [Section 5.3.3](#)).

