6.2.2 Treatment periods

Subjects will be institutionalized on day -1. The following investigations will be performed:

- Physical examination including AE questioning
- Clinical laboratory,

Each subject will receive multiple doses of dabigatran etexilate 220 mg b.i.d. from day 1 to 3 with a single dose on day 4 and from day 8 to 10 with a single dose on day 11, 2 doses of idarucizumab will be administered intravenously approximately 1hour 55 minutes and 2 hours 15 minutes after the last dose of dabigatran etexilate on day 11.

Subjects will be kept under close medical surveillance and will stay in the trial site for at least 72 hours after the idarucizumab dose. Subjects will be allowed to leave the trial site after formal assessment and confirmation of their fitness by the investigator or designee.

The measurements performed during the treatment period are specified under [Section 5.3](#) and in the [Flow Chart](#). For details on time points for all trial procedures, see Flow Chart.

In general, if several measurements including venipuncture are scheduled for the same point of time, venipuncture should be the last of the measurements due to its inconvenience to the subject and possible influence on physiologic parameters.

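### The only scheduled pregnancy test before dosing is at screening, so the pregnancy exclusion can be confirmed at Day 1 allocation on a result up to 28 days old

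*Protocol*

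**What the plan says.** - **Eligibility.** Protocol Section 3.3.3, exclusion 30, bars "Women who are pregnant, nursing, or who plan to become pregnant while in the trial". Section 8.3.1 asks for documented source evidence, before allocation, that no exclusion criterion is met. Section 4.1.3 places allocation on Day 1, before study drug.
- **Scheduled tests.** Section 5.3.3: "A urine pregnancy test will be performed locally on all women of child bearing potential at screening and EOT visits". Section 6.2.1 sets the screening window: "the screening investigations will be performed on 2 to 28 days prior to the first trial drug administration". Flow Chart 2 places EOT at Day 16 to 24.
- **Admission.** Section 6.2.2 says "Subjects will be institutionalized on day -1. The following investigations will be performed" and then lists physical examination with AE questioning, and clinical laboratory. Table 5.3.3: 1, which defines the laboratory tests, contains no pregnancy test. Section 5.3.3 does repeat other checks: "a breath alcohol test and urine drug screen will be performed at screening, on admission".
- **Safeguards.** Inclusion 2 says women of childbearing potential "must be ready and able to use highly effective methods of birth control", with a failure rate below 1% per year. Section 4.2.2.3 obliges them to use the methods given in the subject information. Footnote 9 of Flow Chart 1 requires menstrual changes suggestive of pregnancy to be considered, and allows a further test if the investigator thinks one is appropriate.

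**The concern.** An exclusion criterion that can change between screening and dosing needs evidence that is current when the subject is allocated. Here the plan fixes the moment at which eligibility must be documented but not how recent the pregnancy result must be. A woman who conceives after screening, or whose pregnancy is too early to show at screening, could be allocated on a negative result that no longer holds.

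The stake is subject safety, in a trial whose benefit-risk section states that participants gain no therapeutic benefit. About half of the 12 subjects are to be women, aged 18 to 45. Section 3.3.4.1 has the drug stopped if a subject becomes pregnant, but no test is scheduled between screening and the end of dosing that would bring a pregnancy to light. An exposure would also be an eligibility violation and would start the expedited pregnancy reporting in Section 5.3.6.2.

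**Working it through.** The plan gives no figure of its own on this point, so the check has three parts: the schedule, the age of the last result at each dose, and a rough size for the risk.

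**1. Is any test scheduled between screening and the end of dosing?**

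| Place in the protocol | Day -1 or Day 1 content | Pregnancy test? |
|---|---|---|
| Section 5.3.3, Pregnancy Testing | screening and EOT only | no |
| Section 5.3.3, compliance checks | breath alcohol, urine drug screen on admission | no |
| Section 6.2.2 | physical examination with AE questioning, clinical laboratory | no |
| Table 5.3.3: 1 | routine laboratory list | no |
| Flow Chart 2, Day -1 | vital signs, ECG, laboratory/urinalysis, physical examination, PD | no |
| Flow Chart 2, Day 1 | dabigatran, vital signs, ECG, physical examination, PD, dabigatran PK, urine collection, ADA | no |

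The pregnancy column of Flow Chart 2 is also blank on Days 8 and 11; its one mark is at Day 16 to 24. The rows of Flow Chart 1 are broken in the extracted text, so nothing is inferred from them. The text of Section 5.3.3 settles the point.

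**2. Age of the last scheduled result**

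Screening is 2 to 28 days before Day 1. The second dabigatran course runs "from day 8 to 10 with a single dose on day 11", and idarucizumab is given that same day, 10 days after Day 1. EOT is 15 to 23 days after Day 1.

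- At first dabigatran: 2 to 28 days.
- At idarucizumab: 2 + 10 = 12 to 28 + 10 = 38 days.
- At the next scheduled test: 2 + 15 = 17 to 28 + 23 = 51 days.

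By EOT a subject has had 2 × (3 × 2 + 1) = 14 doses of dabigatran etexilate and 2 × 2500 = 5000 mg idarucizumab.

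**3. Size of the risk**

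Inputs: about 6 women (12 subjects, sex ratio about 1:1), all taken to be of childbearing potential; annual contraceptive failure rate r below 1% (inclusion 2), with 0.1% as an assumed lower value; interval d in days.

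Chance of at least one conception = 1 − (1 − r)^(6d/365).

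- r = 1%, d = 28: 1 − 0.99^(168/365) = 0.46%.
- r = 0.1%, d = 28: 1 − 0.999^(168/365) = 0.05%.
- r = 1%, d = 2: 1 − 0.99^(12/365) = 0.03%.

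The same formula with d = 38 gives 0.06% to 0.63%. That interval is time since the test rather than time at risk, because subjects are confined from Day -1, so 28 days is the relevant upper end.

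The formula covers conceptions after the test. It leaves out a pregnancy already present but too early to detect at screening, for which the documents give no figure.

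**The case against.** The strongest reply is that nothing here is contradictory. An exclusion criterion backed by a screening test is coherent, Section 8.3.1 already demands documented eligibility before allocation, and the protocol has further safeguards. Women must use the listed contraception, menstrual changes must be considered, a further test is allowed, and subjects are under observation from Day -1 until at least 72 hours after idarucizumab. On the protocol's own failure rate the risk is below half a percent, and no estimate depends on it.

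Most of this stands, and it limits the point to how recent the result is. Four stronger readings are tempting but not supported:

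- *Pregnancy status is unverified at dosing.* A screening result exists; it has not been renewed.
- *A pregnant woman would be eligible as written.* Exclusion 30 bars her whatever the date of her test. She might be undetected.
- *A pregnancy could come to light only at EOT.* Over a gap of up to four weeks, footnote 9 could prompt an earlier test, and Section 3.3.4.1 would then apply.
- *The risk is several percent or more because women may start contraception only at screening.* The documents give no per-woman risk of that kind. The methods are set out in subject information that is not among the documents reviewed, so a lead time can be neither assumed nor excluded. The eight-week condition in exclusion 25 applies only to the hormonal option for male subjects' partners.

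What the reply does not answer is that none of the safeguards guarantees a test before the first dose. Footnote 9 gives no time point, Section 8.3.1 does not say how recent the evidence must be and counts a documented verbal account among its acceptable records, and contraception lowers the risk without confirming status.

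**Conclusion.** The point holds as a gap in how recent the evidence for exclusion 30 must be. On the schedule as written, Day 1 allocation can rest on a pregnancy result up to 28 days old, and idarucizumab can follow a result up to 38 days old, with no further scheduled test until dosing is complete.

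The size is small: at most about 0.5% for at least one conception among about 6 women over 28 days. This assumes that all six are of childbearing potential, that contraception is in use throughout and performs no worse than 1% failure per year, and that screening falls at the far end of its window. No endpoint, analysis set or estimate changes. The case for acting is that the harm is serious, participants have no offsetting benefit, and the remedy is cheap. It is a recommended correction.

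**What to change.** Bring the testing schedule into line with exclusion 30 and Section 8.3.1. In Section 5.3.3 and Flow Charts 1 and 2, add a urine pregnancy test at the Day -1 admission for women of childbearing potential, and list it among the admission procedures in Section 6.2.2. State that exclusion 30 is confirmed on that result at Day 1 allocation. The urinalysis sample already scheduled for Day -1 can be used, and Section 5.3.3 already repeats the breath alcohol test and urine drug screen on admission, so no new visit or sampling occasion is needed.

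The cost is about six urine tests, an amendment to the sections named, and an occasional late screening failure. The change checks an existing eligibility criterion and alters no dose, treatment or stopping rule.
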